## 2. Protocol synopsis

Title	Prebiotic Inulin to Limit Antimicrobial-Resistant Infections During Critical Illness: A Phase 2 Clinical Trial
Short title	Inulin in the ICU
Design	Randomized, double-blind, placebo-controlled trial in the ICU
Outcomes	
Primary outcome: Change in relative abundance of SCFA producers through ICU Day 3
 
Secondary outcome: MDRO colonization status on ICU Day 3
 
Additional outcomes:
 
 
1. Feasibility
 
2. Rates of pre-specified AEs
 
3. Antibiotic resistance gene fraction on ICU Day 3
 
4. Culture-proven MDR infections through ICU Day 30
 
5. Fecal SCFA levels
 
6. Proportion of goal calories through ICU Days 3 and 7
 
7. Length of ICU stay
 
8. Length of hospital stay
 
9. Mortality through ICU Day 90
 
10. Self-assessed quality of life at 6 months
 
11. Times series data including ICU Day 7 outcomes
 

Intervention	1:1:1 allocation to inulin 32 g/day, inulin 16 g/day, or placebo dissolved in 250 cc sterile water and given in 2 daily doses for 7 days or until death/hospital discharge
Sample size	90 critically ill patients meeting Sepsis-3 criteria
Eligibility criteria	
Inclusion criteria:
 
 
1. Medical ICU
 
2. Age ≥ 18 years old
 
3. Sepsis, defined according to the Sepsis-3 (2016) consensus as a known or suspected infection with a SOFA score of ≥2 points above baseline
 
4. Broad-spectrum antibiotics, received within the last 24 hours or ordered and pending administration
 
5. Able to complete enrollment within 24 hours of ICU admission for administration of the intervention within 48 hours of ICU admission
 
 
Exclusion criteria:
 
 
1. Inability to receive oral or enteric fluids
 
2. Inulin allergy
 
3. Hyponatremia (serum sodium ≤128 mEq/L)
 
4. Immunosuppression, defined as CD4 count <200 or absolute neutrophil count <500 or reasonable expectation of either during the study intervention period
 
5. Surgery involving the intestinal lumen within 30 days or known intestinal strictures
 
6. Do Not Resuscitate (DNR) or Do Not Intubate (DNI) status, or “no escalation of care” orders
 
7. Lack capacity for consent and no appropriate Legally Authorized Representative (LAR).
 

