### 10.3. Additional outcomes:

10.3.1. *Feasibility.* Descriptive demographic and clinical data will be compared across study groups to assess adequacy of randomization. Summary statistics (count data) will be recorded for patients across all 3 intervention arms to assess feasibility as (1) the enrollment rate (enrolled)/(enrolled+refusals) over each 12 month period; (2) protocol adherence (proportion of randomized subjects who receive 1 or more doses of the allocated intervention); and (3) fidelity of the intervention (defined as the proportion of high/low inulin allocated vs received and also categorically as receipt of 90% or more allocated doses of inulin across groups). Feasibility goals are as stated in Aim 1.

10.3.2. *Rates of pre-specified AEs.* There will be active ascertainment of AEs in the following categories, which will be compared between intervention groups. This will be done through the end of the intervention period (ICU Day 7) and also through Day 30/discharge to assess for delayed AEs.

- Stool frequency, measured by subject or nursing report by the number of spontaneous stools over the 24 hours preceding each assessment;
- Stool consistency, measured by subject or nursing report as an ordinal variable (0-4) over the 24 hours preceding each assessment;

- Abdominal bloating, measured by subject or nursing report as an ordinal variable (0-3) over the 24 hours preceding each assessment.
- Electrolyte abnormalities, measured by examining for differences in median values, minimum/maximum values, and proportions of values outside the normal range. This will be done for glucose, calcium, magnesium, phosphate, potassium, and sodium.
- Nausea, vomiting, obstruction, and abdominal pain. These will be recorded as present or absent based on bedside assessment of the subject or based on the nursing impression.
- Culture-proven infections, which will be considered both an AE and an outcome (see 10.3.4).

10.3.3. *Antibiotic resistance gene fraction on ICU Day 3.* DNA will be extracted from rectal swabs (MoBio PowerFecal, Carlsbad, CA) and assessed using multiplex quantitative PCR (Qiagen Cat. No. 330261, Valencia, CA) for 87 common antibiotic resistance genes. Within-individual differences in multiplex qPCR results will be compared from baseline to Day 3 both as summed changes and within relevant gene categories (e.g.,  $\beta$ -lactamase resistance genes) and compared between intervention groups.

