10.3.4. *Culture-proven MDR infections through ICU Day 30.* Antibiotic-resistant infections will be defined as those showing all of the following: (1) site-specific symptoms or signs of infection, (2) initiation of targeted antimicrobials by the treating ICU team, and (3) molecular diagnostics or cultures showing an MDRO as adapted from the CDC and NHSN and previously used by our group (**Table 4**). Rates of infections will be compared between intervention groups as a sum total, and separately for 3 distinct periods: the intervention period of Day 0 to 7, the Day 7 to 30 period, and the Day 30 to 6 month period.

**Table 4. Criteria used to adjudicate culture-proven MDR infections for.** Criteria based on CDC/NHSN guidelines.

Criteria	Operationalization	Example
1. Site-specific symptoms or signs of infection.	
 
• Pulmonary: documentation of new or worsening cough or imaging consistent with an infection
 
• Urinary: fever, dysuria, increased urinary frequency, flank pain, mental status changes, or hypotension and clinical exclusion of other causes for infection.
 
• Bloodstream: clinical evidence of a bloodstream infection (fever, chills, or hypotension) without alternative sources for infection
 
• Stool: documentation of new loose stools or frequent stools <math>\geq 3</math> per 24 hours
 
• Wound: appropriate surgical site incision or wound with discharge, warmth, or erythema.
 
	Cough and a chest X-ray showing new infiltrate.
2. Positive cultures or other diagnostics with an MDRO.	
 
• Pulmonary: quantitative or semi-quantitative sputum or bronchoscopic cultures
 
• Urinary: <math>\geq 10^5</math> CFU/mL growth.
 
• Bloodstream: growth of a recognized bloodstream pathogen from blood but not another site or growth of a NHSN commensal from blood but not another site.
 
	Sputum culture growing $>10^5$ CFU/ml of K. pneumoniae resistant to ceftriaxone.

- Stool: positive PCR for the *C. difficile* toxin B gene (Cepheid or BioFire) or positive toxin B EIA
- Wound: growth of aseptically obtained organisms.

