## 17. Statistical methods

### 17.1. Overall plan for statistical analysis

After enrollment is complete, the REDCap dataset will undergo DCC cross-checks for quality and accuracy. The PI will review blinded data to identify errors which, if they exist, will be rectified by reference to paper CRFs or to the EMR. After quality checks are complete, the REDCap dataset will be closed and locked. The biostatistician will then perform an intent-to-treat analysis to determine the primary and secondary outcomes. The DSMO will have complete access both to the raw data and to the analytic code used by the biostatistician and will nominate a qualified monitor who will review this work for rigor. Once this is complete, the primary and secondary outcomes will be finalized. At this point, the locked data will be made available to the PI and other investigators for additional analyses. For all analyses,  $\alpha < 0.05$  will be considered statistically significant and two-sided testing will be performed. When death is a competing risk, Fine and Gray regression analyses will be performed.

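### Section 17.1 applies one rule, two-sided 0.05 is significant, to the additional outcomes as well, with no multiplicity control and no general statement that they are exploratory

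*Combined protocol and SAP*

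**What the plan says.** The synopsis and section 10 sort outcomes into primary, secondary and additional. The synopsis numbers eleven additional outcomes, the last being "Times series data including ICU Day 7 outcomes". Section 17.1 has the biostatistician analyse the primary and secondary outcomes first and has that work independently checked. Once those two are final, "the locked data will be made available to the PI and other investigators for additional analyses". The rule that follows covers all analyses without distinction: results below 0.05 "will be considered statistically significant and two-sided testing will be performed".

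Section 10.3 describes the additional outcomes. Feasibility is descriptive: "Summary statistics (count data) will be recorded for patients across all 3 intervention arms to assess feasibility". The other ten are compared between arms, most in several ways. MDR infections, for example, are compared "as a sum total, and separately for 3 distinct periods". Electrolytes are "measured by examining for differences in median values, minimum/maximum values, and proportions of values outside the normal range", for six analytes. The adverse-event comparisons cover two windows: "This will be done through the end of the intervention period (ICU Day 7) and also through Day 30/discharge to assess for delayed AEs".

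Exploratory language appears only for semi-quantitative culture (13.2 and 17.2), Day 7 MDRO status (17.2) and a possible delayed effect (10.3.11). No different significance rule goes with it. Section 17.3 gives power for the primary and secondary outcomes only.

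**The concern.** A threshold of 0.05 applied to many outcomes without limit produces significant results by chance. The trial aims for 90 evaluable patients and has no power calculation for any additional outcome. Even so, a p-value below 0.05 for MDR infections in one period, mortality at one time point or one fecal SCFA could be reported as statistically significant under the plan's own rule. These clinical results are the ones most likely to be quoted, above all if the primary microbiome outcome is null. Section 17.3 expects promising results to lead to larger trials but does not define promising, so a chance finding could carry more weight than it deserves.

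**Working it through.** **The plan's own figures.** The documents state no number of comparisons, family-wise error or expected number of false positives, so there is nothing of that kind to reproduce. The power statements in 17.3 for the primary outcome do reproduce at an unadjusted two-sided 0.05. With 30 versus 30 and 0.73 SD, the noncentral t gives 79.4%; with 30 versus 60 and 0.63 SD, 79.6%. Both match the stated 80%. So 0.05 is a per-test level.

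**Comparisons outside adverse events (10.3.3 to 10.3.10), one test each:**
- resistance genes: summed change plus at least one gene category (number not stated), at least 2
- MDR infections: total plus three periods, 4
- fecal SCFAs: butyrate, acetate, propionate, 3
- goal calories: Day 3 and Day 7, 2
- ICU stay and hospital stay, 2
- mortality: 30 and 90 days, 2
- quality of life: EQ-5D-5L and Katz ADL at 3 and 6 months, 4

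Sum: 2 + 4 + 3 + 2 + 2 + 2 + 4 = 19.

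Expected false positives under no effect: 19 × 0.05 = 0.95. This does not depend on correlation between tests. Chance of at least one, if independent: 1 − 0.95^19 = 0.62.

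**Sensitivity of that count.**
- One resistance-gene test and quality of life at 6 months only: 16 comparisons, 0.80 expected, 56% if independent.
- Two time-series tests added (assumed to be SCFA producers and MDRO status at Day 7): 21 comparisons, 1.05 expected, 66% if independent.

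**Adverse events (10.3.2), if tested.** Per window: stool frequency, stool consistency and bloating (3); six analytes × four summaries (24); four symptoms; infections (1). Over two windows: 2 × (3 + 24 + 4 + 1) = 64.

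**Totals with adverse events:**
- without the time series: 64 + 19 = 83; 83 × 0.05 = 4.15
- with two time-series tests: 64 + 21 = 85; 85 × 0.05 = 4.25
- minimum and maximum as one summary, otherwise as in the 85: 2 × (3 + 18 + 4 + 1) + 21 = 73; 73 × 0.05 = 3.65
- narrowest reading (minimum and maximum as one summary, infections not counted again as an adverse event, no time series, one resistance-gene test, quality of life at 6 months only): 2 × (3 + 18 + 4) + 16 = 66; 66 × 0.05 = 3.3

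**What moves these figures.** Testing three arms and then pooled inulin against placebo, as 17.2 does for the primary and secondary outcomes, would add comparisons. Fisher tests on sparse events reject less often than 0.05: with 30 versus 60 patients, 0.023 at a 5% event rate and 0.031 at 10%. That lowers the expected number somewhat.

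**The case against.** The strongest reply is that the plan already has a hierarchy. Outcomes are tiered, the primary and secondary are finalised before the rest are opened, and only those two are powered. Section 17.2 also takes the effect size for future trials from Day 3 MDRO colonization, not from whichever additional outcome looks best. All of this is true, and it limits the harm. It does not limit the significance rule, which 17.1 applies to all analyses.

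A reader might infer that more than 80 tests are planned, that four false positives are expected and that a false finding is almost guaranteed. The documents do not support that as the main claim. The count is a reconstruction, and it falls to 66 on the narrowest reading. In the count of 83, 64 are adverse-event items. Section 10.3.2 says these will be compared but names no test, and section 15 describes adverse-event reporting as patient-level means, minima and maxima for the monitoring committee. Safety action runs through that committee and the toxic-death boundary in 17.4, not through p below 0.05. Formal error control across adverse events is often not wanted in any case.

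A reader might also take ten tested outcomes and quote 1 − 0.95^10 = 40%. That figure assumes independence, and stay, mortality and infection in the same patients are related. The 62% above carries the same caveat. The expected count does not.

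**Conclusion.** The concern holds in a limited form. Section 17.1 lets a nominal result on any tested additional outcome be called statistically significant, with no multiplicity control. Most of those outcomes carry no exploratory label. Outside adverse events, about one false significant result is expected if inulin has no effect (0.95 from 19 comparisons; 0.80 to 1.05 over the readings shown). This assumes one test per named comparison, each at its nominal level. With adverse events tested as well, the expected number is about 3 to 4.

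The primary analysis is unaffected. Nor does the point show that the secondary outcome must be gated on the primary, as a reader might infer. MDRO colonization has its own power calculation in 17.3, and gating would remove its significance claim whenever the primary failed. The problem with the additional outcomes does not justify that cost.

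**What to change.** In 17.1, replace the rule for all analyses with three statements:
- The 0.05 significance rule applies to the primary and secondary outcomes.
- The additional outcomes are exploratory and are reported as between-arm estimates with 95% confidence intervals, without significance claims.
- Adverse events are summarised by arm with differences and intervals, so that safety signals stay visible.

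This is a change of wording only; data collection, sample size and procedures stay as they are. The cost is that a nominal p below 0.05 on an additional outcome, such as MDR infection or mortality, can no longer be claimed as significant. While the sentence is open, the two-sided 0.05 should also be reconciled with 17.3, which sizes the secondary outcome at one-sided 0.10. That is a separate point, and this fix does not settle it.

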### 4. Funding

This project is funded by a Department of Defense Peer-Reviewed Medical Research Program Clinical Trial Award (PR181960) recommended for funding on February 20, 2019.

#### 4.1 Role of funding bodies

The study will be designed and conducted, and the results analyzed, presented, and published by the investigators independent of the funding bodies.

### 5. Background and rationale for study

#### 5.1 Background

Multidrug resistant (MDR) bacterial infections are a leading cause of morbidity, death, and healthcare-associated costs. Nowhere is this more important than in the intensive care unit (ICU), where over half of all infections are MDR^4 and where sepsis from MDR bacteria confers 10-20% absolute increased mortality.

This project hypothesizes that antibiotic resistance in the ICU is a problem of the human gastrointestinal microbiome, which is the critical reservoir for the bacteria and plasmids that encode antibiotic resistance genes. The normal gut microbiota prevents colonization and subsequent infection with MDR organisms through competition for scarce resources and other mechanisms. In the setting of critical illness, normal colonization resistance is lost and there are no currently available therapies to restore it.

Specific gut bacteria contribute to colonization resistance. ICU patients have low levels of butyrate and other short chain fatty acids (SCFAs) which are derived from dietary fiber by anaerobic bacteria primarily within the Clostridial Clusters IV and XIVa (e.g., *Faecalibacterium prausnitzii*). SCFAs moderate colonic inflammation, enlarge the pool of regulatory T cells, and

contribute to the thickness of the colonic mucus layer and pathogen resistance. During critical illness, levels of SCFA-producing bacteria and SCFAs are low, and these levels further decline with antibiotic treatment. Loss of SCFA-producing bacteria correlates with an increase in colonization with vancomycin-resistant *Enterococcus* and other antibiotic-resistant pathogens. We believe that preservation of SCFA-producing bacteria during critical illness is of major importance and can prevent the proliferation of colonizing organisms with antimicrobial resistance.

The prebiotic fiber **inulin** is a vegetable-derived polysaccharide that restores gastrointestinal colonization resistance against MDROs. SCFAs cannot be easily given to humans due to oral intolerance and rapid metabolism, but inulin promotes growth of SCFA producers to raise SCFA levels. In animals, inulin-type fibers improve survival after pathogen challenge even in the face of antibiotics. In a randomized trial of 30 outpatients, inulin increased fecal levels of SCFA producers by 35-90%, with a 3-fold decrease of serum markers of bacterial translocation (e.g., lipopolysaccharide) relative to placebo. Inulin is safe in ambulatory patients with biologic effects seen at 16 g/day. In the ICU, inulin-type fibers have been given up to 36 g/day without adverse events and in our ICU cohort we have observed 30 g/day dietary fiber without intolerance. This trial will test whether inulin supplementation has similar effects in the ICU as it does in animal models and as it appears to in healthy volunteers: will it result in higher levels of SCFA-producing Clostridia, decreased gastrointestinal antibiotic resistance and lower risk for MDR infections?

## 5.2 Trial purpose and design

The purpose of this Phase 2 trial is to determine the feasibility and safety of inulin for the prevention of antibiotic resistant infections or colonization in critically ill patients. We will perform a double-blind, randomized controlled trial of inulin in the ICU with three arms (placebo, inulin 8 g twice daily, and inulin 16 g twice daily). Subjects will be treated with inulin or placebo for 7 days with bedside follow-up for 30 days or hospital discharge and with long-term telephone follow-up for 6 months.

## **6. Previous data**

Our observational ICU data supports the importance of SCFA producers in the ICU. In animals, inulin protects against sepsis. Inulin increases SCFA producers in ambulatory studies and inulin-like fibers are safe in the ICU setting.

[figure not shown]
### 6.1 Evidence supporting the importance of SCFA producers in the ICU

We have assembled two large prospective cohorts now totaling over 500 ICU patients who have contributed rectal swabs and other data. Results from these cohorts confirm the importance of SCFA producers in protecting against pathogen colonization and infection in the ICU.

- **Cohort #1.** A single rectal swab was performed on medical ICU admission for consecutive patients. Swabs were cultured for VRE and residual DNA was extracted for 16S rRNA gene sequencing; patients were then followed for up to 30 days for death or culture-proven infections. In 9 months, **301 patients** were enrolled of whom 91 (30%) were VRE colonized. Thirty-day mortality was 25% and an overlapping 21% patients developed culture-proven MDR infections.

Cohort #1 demonstrated that the bacteria causing infections in the ICU are present as gut colonizers at the time of admission. We tested whether colonizing MDROs predicted subsequent death or culture-proven infection. Presence of the colonizing organism at ICU admission was almost always associated with subsequent organism-specific infection, even after adjusting for

acute severity illness as captured by the Simplified Acute Physiology Score-3 (SAPS-3) and other relevant clinical variables. This was true for VRE (aHR 5.85, 95% CI 2.25-15.2, 16 infections), *C. difficile* (aHR 19.0, 95% CI 4.40-81.8, 9 infections), *Pseudomonas* (aHR 2.37, 95% CI 1.04-5.43, 28 infections), and *Klebsiella spp.* (aHR 3.81, 95% CI 1.10-13.2, 28 infections). To interrogate the process by which MDRO colonization may lead to infection, we also examined MDRO domination defined as  $\geq 30\%$  16S reads corresponding to a potential pathogen. Because this cohort contained VRE culture data, we were able to test whether patients who had *Enterococcus* domination were in fact colonized by VRE. *Enterococcus* domination (15% of the cohort) and VRE colonization (30%) both predicted *all-cause* infection (**Figure 1**). When 30-day mortality was examined as a stand-alone outcome, VRE colonization/domination predicted 40% increased mortality, after adjusting for SAPS-3 score and other factors.

[figure not shown]

**Figure 1. VRE colonization/domination was associated with death or culture-proven infection in the ICU.** VRE colonization or domination was assessed at the time of ICU admission and patients were followed for all-cause culture-proven infection.

Next, we sought to determine the relationship between SCFA producers and VRE based on culture at the time of ICU admission. Only VRE was cultured within this cohort, so we did not have the ability to assess colonization with other MDROs using culture (e.g., Gram negative bacteria). Based on the 16S sequencing results, SCFA producers were classified as absent (<.01% relative abundance), low (.01% to 1%), or high (>1%) after Haak *et al.* High levels of SCFA producers were associated with lower prevalence of VRE colonization based on culture: 40% when SCFA producers were absent, 27% when they were low, and 22% when they were high ( $p < .01$ ). Results were similar for *Enterococcus* domination.

- **Cohort #2.** This cohort was designed to examine *dynamic* changes in the ICU microbiome, focusing on SCFA producers and MDROs. Swabs were performed in duplicate at ICU admission and 72 hours later ( $\pm 4$  hours). Swabs were then (1) cultured for MRSA, VRE, and MDR Gram negatives and (2) 16S sequenced. In 3 years, **230 patients** out of a target of 300 have been enrolled with 126 sequenced to date.

Cohort #2 demonstrated that SCFA-producing bacteria associate with preserved colonization resistance. Within cohort #2, we first performed an unbiased analysis using LEfSe to ask which bacterial taxa changed most within individuals, comparing their admission and Day 3 samples. 14 taxa were identified as having significantly changed at a false-discovery adjusted  $p < .05$ . Ten taxa decreased over these first 72 hours of which 6 were SCFA producers. These changes were substantial in magnitude (e.g., 8-fold for *F. prausnitzii*).

[figure not shown]

**Figure 2. Higher levels of SCFA-producing bacteria associated with lower colonizing MDROs, both at the time of ICU admission and 72 hours later.** Lines are 95% confidence estimates.

We wanted to know how SCFA producers associated with MDRO colonization. SCFA producers were again classified as absent, low, or high based on sequencing. MDROs were classified as present vs absent based on culture results. At both ICU admission and 72 hours later, there was a stepwise relationship

where higher SCFA producers was associated with decreased MDRO colonization (**Figure 2**, previous page). Comparing high to absent SCFA levels, the difference in rates of MDRO colonization was over 25%.

Last, we sought to retrospectively assess the impact of dietary fiber on SCFA producers and MDROs. Observed fiber intake was low overall with a mean of 13.4 g over 72 hours, but some patients did receive large amounts of fiber (maximum 30 g/24 hours). There was no intolerance of fiber based on documentation of abdominal distension, diarrhea, or nausea/vomiting. Fiber intake was classified into tertiles and SCFA producers were examined as a continuous measure based on 16S sequencing. At ICU admission, baseline relative abundance of SCFA producers was similar across fiber intake groups. After 72 hours, higher fiber intake was associated with higher levels of SCFA producers (**Figure 3**). Higher fiber was also associated with less *Enterococcus* (median abundance .08% high fiber vs .35% no fiber,  $p=.03$ ). This data is observational so there were baseline patient differences between those who did and did not receive high dietary fiber. To account for this, we built a multivariable model adjusted for acute severity of illness, receipt of antibiotics, and total caloric intake. In this model, there was a 0.30% median increase in SCFA producers after 72 hours per additional 10g of fiber intake ( $p<0.01$ ). This suggests that dietary fiber has the potential to impact levels of SCFA producers, even during critical illness and with receipt of broad-spectrum antibiotics (78% of the cohort).

**Figure 3. Higher fiber intake associated with higher levels of SCFA producers in the ICU.** Fiber intake was classified into tertiles, with relative abundance of SCFA producers classified based on 16S sequencing.

